2.2 Analysis sets

All screened patients (SCR): The SCR set comprises all patients who were screened.

Full analysis set (FAS): The FAS comprises all randomized patients with assigned treatments. Patients will be analyzed according to the randomized treatment assignment following the intention-to-treat (ITT) principle, even if they actually received no or a different treatment.

The FAS will be used for the summary of demography and baseline characteristics as well as for all efficacy analyses.

Per-protocol set (PPS): The PPS is a subset of FAS, consists of all randomized patients who take at least one dose of study medication and have no major protocol deviations that could confound the interpretation of analyses conducted on the FAS. Major protocol deviations will be determined according to the pre-defined protocol deviation criteria before treatment unblinding (e.g. non-compliance for a large proportion of the time in study). For analyses performed on the PPS, only efficacy data assessed during the on treatment period (as defined in [Section 2.1.1](#)) will be included.

The PPS will be used for the supportive analyses of the primary efficacy variable and selected key secondary variables.

Safety set (SAF): The SAF set includes all patients who received at least one dose of study medication. Patients will be analyzed according to the actual treatment received. If patients received both investigational drug and active comparator accidentally during the study, they

will be analyzed according to the treatment to which they were exposed longer in duration. The SAF will be used for all safety analyses.

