2.6 Analysis of the key secondary objectives

2.6.1 Key secondary endpoints

2.6.1.1 Disability worsening (3-month or 6-month confirmed)

A 3-month confirmed disability worsening (3mCDW) is defined as an increase from baseline in EDSS sustained for at least 3 months. Analogously, a 6-month confirmed disability worsening (6mCDW) is defined as an increase from baseline in EDSS sustained for at least 6 months. This means that after a scheduled or unscheduled visit at which the patient fulfills the disability worsening criterion as defined in [Table 2-13](#), all EDSS assessments (scheduled or unscheduled) need to also fulfill the worsening criteria until the worsening ("the event") can be confirmed at the first scheduled visit that occurs in the absence of (confirmed or unconfirmed) relapse 3 months/90 days (or 6 months/166 days) after the onset of the worsening, or later.

In the time to event (3mCDW or 6mCDW) analysis, time will be calculated as (the date of EDSS assessment at onset of the event – date of first administration of study drug+1) for patients with the events. Censoring occurs in those patients who did not experience an event in the study (during the treatment epoch), this includes patients who had a "tentative" disability worsening that could not be confirmed due to an early discontinuation or any another reason. The censoring time is calculated as (the date of last EDSS assessment during the treatment epoch – date of first administration of study drug+1). Additional details are provided in footnote of Table 2-13.

Table 2-13 Criterion for disability worsening based on change in EDSS score

Total EDSS at baseline*	"Disability worsening" criterion
0	$\geq +1.5$

0.5 to 5	$\geq +1$
≥ 5.5	$\geq +0.5$

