
A 3-month confirmed disability worsening can have an onset at any scheduled or unscheduled visit if the disability worsening criterion is met. A disability worsening can only be confirmed at a scheduled visit in the absence of (confirmed or unconfirmed) relapse if, over a period of 3 months (≥ 90 days=3×30) time interval, all assessments meet the worsening criterion.
 
A 6-month confirmed disability worsening can have an onset at any scheduled or unscheduled visit if the disability worsening criterion is met. A disability worsening event can only be confirmed at a scheduled visit in the absence of (confirmed or unconfirmed) relapse if, over a period of 6 months (≥ 166 days=$6 \times 30 - 14$ [visit window]) time interval, all assessments meet the worsening criterion.
 
If a patients dies due to MS (EDSS=10 at any time), it will be considered a confirmed disability worsening regardless of the baseline EDSS or the change in EDSS. The time will be calculated as (date of EDSS assessment at a tentative onset of the event – date of first administration of study drug+1) or (date of death – date of first administration of study drug + 1) if a tentative onset date does not exist. Note: Death for other reasons than MS (i.e. not EDSS=10) will not be considered a disability worsening.
 
*Baseline EDSS is defined as the last EDSS assessment prior to the first dose of study medication (protocol inclusion criterion is EDSS 0-5.5)
	

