- Time to 6-month confirmed worsening of at least 20% in the timed 25-foot walk test (T25FW): similar to definition of 6mCDW ([Section 2.6.1.1](#)) but replacing the worsening criteria by at least 20% increase from baseline in T25FW score. Patients who do not reach the endpoint by the end of treatment epoch date will be censored at date of last T25FW assessment during the treatment epoch.
- Time to 6-month confirmed worsening of at least 20% in the 9-Hole Peg Test (9HPT): similar to definition of 6mCDW ([Section 2.6.1.1](#)) but replacing the worsening criteria by at least 20% increase from baseline in 9HPT score in at least one hand. Patients who do not reach the endpoint by the end of treatment epoch date will be censored at date of last 9HPT assessment during the treatment epoch.

- 6mCDI sustained until EOS: same as 6mCDI except that the rest EDSS scores (scheduled or unscheduled) after the confirmation visit of the 6mCDI during the treatment epoch have to meet the disability improvement criteria as well.
- Disability status during the study (classified as improved, stable, or worsened): patients will be classified as improved if 6mCDI sustained until EOS was met (regardless whether 6mCDW status was met at an earlier time point); or classified as stable if 6mCDW was not met & 6mCDI sustained until EOS was not met; or classified as worsened if 6mCDW was met & 6mCDI sustained until EOS was not met.
- MS relapse characteristics include severity, recovery, hospitalization, and steroid treatment. The severity of MS relapses will be derived according to the criteria in [Table 2-15](#). All relapses (confirmed or unconfirmed) will be considered. For confirmed relapses, the EDSS used to confirm the relapse (as specified in [Section 2.5.2](#)) will be used to determine the severity. For unconfirmed relapses, all EDSS assessments taken within 30 days from the relapse start date and before the relapse end date will be checked among which the most severe case will be selected to determine the severity. If no such EDSS assessment is available, the severity will be set to “missing EDSS”. If none of such EDSS assessments meet the mild, moderate or severe conditions, the severity will be set to “no worsening in EDSS”.

Table 2-15 Severity of MS relapse

Mild relapse	Moderate relapse	Severe relapse
EDSS increase of 0.5 point	EDSS increase of 1 or 2 points	Exceeding Moderate criteria
or	or	or

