- The disability status during the study will be summarized descriptively by treatment group (i.e., number and percent of patients improved, stable or worsened will be provided) and compared between treatment groups via a Chi-square test.
- For MS relapse characteristics, summary statistics will be presented. The proportion of patients hospitalized for relapse and the proportion of patients with severe relapses will be compared between treatment groups using a Chi-square test.
- For the presentation of descriptive statistics, ARR time based and ARR patient based will be reported by treatment group.

- Change in T2 lesion volume on MRI will be summarized by visit-window. Cross-sectional analyzes will be done by using a rank ANCOVA with treatment and region (factors), and baseline T2 volume as a continuous covariate.
- Number of new or enlarging T2 lesions on MRI between EOS and Month 12 will be analyzed in a negative binomial regression model, and presented similarly to that used for the annualized rate of new or enlarging T2 lesions. The number of new T2 lesions on the EOS scan relative to the Month 12 scan will be used as the response variable. The natural log of the time (in years) from the Month 12 scan to the EOS MRI scan will serve as the offset variable.
- Number of new or enlarging T2 lesions on MRI at yearly visits relative to baseline will be analyzed in a negative binomial regression model and presented similarly to that used for the annualized rate of new or enlarging T2 lesions. The number of new T2 lesions on the yearly MRI scan relative to the screening scan will be used as the response variable. The natural log of the time (in years) from the screening scan to the yearly MRI scan will serve as the offset variable. Due to the variable length of patient study participation, this analysis will only be performed for visits where there are at least a total of 100 patients with non-missing data on this endpoint. In case of non-convergence, region will be removed from the regression model.
- The analysis of ARBA is described in ([Section 2.6.2.6](#)) as supportive analysis to the key secondary endpoint of brain volume change.

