2.7.3 Handling of missing values/censoring/discontinuations

As a general rule, missing data will not be imputed in any secondary endpoint analyses. All the available data up to the end of treatment epoch date, irrespective of on or off study treatment will be used as applicable. Details of handling discontinuations or censoring are provided in the relevant endpoints or analysis of endpoints sections ([Section 2.7.1](#) and/or [Section 2.7.2](#)).

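### 'Stable' disability status is whatever remains after confirmed worsening and sustained improvement, so patients who could not be assessed, or whose change was unconfirmed at their last EDSS, are reported and tested as stable

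*SAP*

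**What the plan says.** SAP 2.7.1 defines disability status during the study. Improved means that a 6mCDI sustained to EOS was met. Worsened means that 6mCDW was met without a sustained 6mCDI. Everyone else is "classified as stable if 6mCDW was not met & 6mCDI sustained until EOS was not met".

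Both component events need a change held for at least 166 days and confirmed at a scheduled visit (SAP 2.6.1.1 and 2.6.1.2). Worsening must also be confirmed outside a relapse. The time-to-event analysis censors a tentative "disability worsening that could not be confirmed due to an early discontinuation or any another reason". There is one exception to the confirmation rule: if a patient dies of MS, "it will be considered a confirmed disability worsening regardless of the baseline EDSS or the change in EDSS". Death from other causes is not a worsening.

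On population, SAP 2.2 states: "The FAS will be used for the summary of demography and baseline characteristics as well as for all efficacy analyses". On analysis, SAP 2.7.2 states: "The disability status during the study will be summarized descriptively by treatment group", and the categories are "compared between treatment groups via a Chi-square test". On missing data, SAP 2.7.3 states: "As a general rule, missing data will not be imputed in any secondary endpoint analyses". It refers back to 2.7.1 and 2.7.2 for discontinuations, and those sections add nothing for this endpoint.

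**The concern.** The label reads as a finding about the patient, but the rule needs no finding. On the FAS these patients are all called stable:

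- those with no post-baseline EDSS;
- those who leave before any 166-day confirmation is possible (MS deaths apart);
- those who die of another cause without an earlier confirmed event;
- those whose last EDSS meets the worsening or improvement criterion but was not confirmed, and who had no earlier qualifying event.

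In the Cox models such patients are censored, which treats their outcome as unknown. The status table has no counterpart to censoring, so unknown becomes stable. The same SAP section handles comparable gaps elsewhere. NEDA-4 requires follow-up to the time point, with a dropout sensitivity analysis in 2.7.2, and relapse severity has a separate level for a missing EDSS.

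At stake is a percentage stable that partly reflects absence of data. If dropout differed by arm, the chi-square test would also respond to that difference.

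**Working it through.** **The plan's own figure.** The documents give no expected proportion or power for disability status, so the check starts from its component, 6mCDW (SAP 3.1.7).

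- Hazard ratio: ln(1 − 0.07548)/ln(1 − 0.12) = 0.614, as stated.
- Events at one-sided alpha 0.024375 and 80% power: 4 × (1.971 + 0.842)² / (ln 0.614)² = 133, as stated.

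**Inputs.**

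- Dropout of 20% over 2 years (SAP 3.1.7): d = −ln(0.8)/2 = 0.1116 per year.
- 6mCDW risk of 12% over 2 years (SAP 3.1.7): l = −ln(0.88)/2 = 0.0639 per year, used as a proxy for the onset hazard.
- Confirmation time (SAP 2.6.1.1): c = 166/365.25 = 0.4545 years.
- Assumed here: exponential onset and dropout, independent of each other; every observed worsening persists; follow-up either fixed at T = 1.5 years or uniform over 1 to 2 years with visits every 84 days.

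**Too early for any 6-month confirmation.** 1 − exp(−0.1116 × 0.4545) = 4.9%. With 10% or 30% dropout the figure is 2.4% or 7.8%.

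**Observed but unconfirmed worsening, T = 1.5 years, teriflunomide rate.**

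- Observed onset: l/(l+d) × [1 − exp(−(l+d)T)] = 0.3642 × 0.2314 = 8.4%.
- Confirmed: exp(−dc) × l/(l+d) × [1 − exp(−(l+d)(T−c))] = 0.9506 × 0.3642 × 0.1676 = 5.8%.
- Unconfirmed, hence stable: 2.6%, about 31% of observed onsets.
- At the ofatumumab rate: 5.3% observed, 3.6% confirmed, 1.7% unconfirmed, again about 31%.

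Simulation with uniform 1 to 2 year follow-up and 84-day visits gives 7.7% observed, 5.1% confirmed and 2.6% unconfirmed. The 4.9% and 2.6% groups overlap and should not be added.

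**Source of the 2.6%.** Onsets in the last 166 days among patients who reach T: exp(−dT) × [exp(−l(T−c)) − exp(−lT)] = 0.8459 × (0.9354 − 0.9086) = 2.3%. So about 2.3 of the 2.6 points come from end-of-study truncation, which affects both arms, and not from dropout. Consistently, the simulated figure barely moves with dropout: 2.7% at 10% and 2.6% at 30%.

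**Effect on the test.** Take identical hazards in both arms, worsened v not worsened, 450 per arm, T = 1.5 years.

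- Equal 20% dropout: both arms 5.8% worsened, so rejection stays at about 5%.
- 15% v 30% dropout (assumed): 5.98% v 5.44% worsened; SE = √(0.0571 × 0.9429 × 2/450) = 0.0155; z = 0.35; two-sided rejection Φ(−1.61) + Φ(−2.31) = 6.4%.
- 10% v 30% dropout (assumed): 6.14% v 5.44%; SE = 0.0156; z = 0.45; rejection Φ(−1.51) + Φ(−2.41) = 7.3%.

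Simulation with uniform follow-up gives 6.2 to 6.5% and 7.3 to 7.6%.

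**The case against.** The strongest reply is that little depends on this table. Disability status is not among the secondary objectives in Protocol 2.2 or SAP 1.2.3, and it lies outside the multiplicity procedure. 6mCDW, 6mCDI and sustained 6mCDI are each analysed by Cox models with censoring. SAP 2.6.2.1 adds sensitivity analyses that count deaths and lack-of-efficacy withdrawals as worsening. The plan assumes equal dropout and asks patients who stop drug to remain in the study. SAP 2.3.1 reports study discontinuation by arm, so an imbalance would be seen. All of this stands and limits the weight of the point. None of it changes what the rule does.

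Four stronger readings are tempting, and the documents do not support them.

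- **That 7.4% are stable by construction.** This counts everyone who leaves before day 252, the first 84-day visit able to confirm an onset first seen at day 84. But onset may be recorded at an unscheduled visit, the SAP counts EOS as a nominal visit, and an EOS visit is required at withdrawal. The strict floor is 4.9%.
- **That a third of worsenings are hidden.** This assumes that every tentative worsening would have persisted. The confirmation rule exists because some do not.
- **That error inflation reaches about 8 to 10%.** This needs 900 per arm as well as the assumed unequal dropout. SAP 3 says other secondary efficacy endpoints are analysed by study, and 2.7.2 specifies no pooling for this one.
- **That the rule contradicts SAP 2.7.3.** No missing EDSS value is filled in. The label records only that no confirmed event was observed.

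**Conclusion.** The point holds as a labelling fault in a supplementary table. As written, stable mixes patients observed to be stable with patients whose status is unknown or whose change was unconfirmed, and nothing elsewhere in the SAP separates them.

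Under the plan's own dropout and event rates, about 4.9% of randomized patients leave before day 166. About 2.6% have an observed worsening that is counted as stable, against 5.1% counted as worsened. These figures rest on independent exponential dropout and onset. The 2.6% and 5.1% also assume uniform 1 to 2 year follow-up and 84-day visits. The 2.6% is an upper bound on hidden worsening.

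A reader might infer that the chi-square comparison is biased by design. It is not: with the plan's equal dropout it keeps about 5% error. It reaches about 6.5% or 7.6% at 450 per arm only with dropout of 15% v 30% or 10% v 30%. Those rates appear in neither document, and the calculation uses worsened v not worsened, whereas the plan tests three categories. The confirmatory results are untouched. This is a minor point.

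**What to change.** In SAP 2.7.1, restrict stable to patients with enough scheduled EDSS follow-up for a 166-day confirmation and no unconfirmed worsening or improvement at their last EDSS. Add two rows, reported by arm on the FAS denominator: unconfirmed worsening or improvement at last EDSS, and not evaluable.

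In SAP 2.7.2, keep all FAS patients in the main chi-square comparison with the added categories. Show two sensitivity analyses: the test on evaluable patients only, and an all-FAS version that counts unconfirmed worsening as worsened. The evaluable-only test should not be the main one, because evaluability is determined after randomization and the restriction departs from the FAS rule in SAP 2.2.

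The cost is one derivation from EDSS data already collected, a few more table rows and a lower reported percentage stable. The Cox analyses and the multiplicity procedure do not change.

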2.7.2 Statistical model and method of analysis

Methods of analyses for efficacy endpoints defined in [Section 2.7.1](#) are described below.

- The analysis of “Time of first relapse” and “Annualized relapse rates > 8 weeks after the onset of treatment” is described in ([Section 2.5.5](#)) as sensitivity analysis to the primary analysis.
- The analysis of the “Risk of a 3mCDW > 8 weeks after the onset of treatment” and “Risk of a 6mCDW > 8 weeks after the onset of treatment” is described in ([Section 2.6.2.1](#)) as a supportive analysis to the key-secondary 3mCDW and the 6mCDW, respectively.
- Time to 6mCCD will be analyzed in the combined FAS from studies G2301 and G2302, in a Cox proportional hazards model with study as stratum, treatment, and region as factors and baseline SDMT-result as a continuous covariate. By study analysis will be performed for information only.
- Time to 6mCDW or 6mCCD (composite endpoint) will be analyzed in the combined FAS from studies G2301 and G2302, in a Cox proportional hazards model with study as stratum, treatment, and region as factors and baseline EDSS and baseline SDMT scores as continuous covariates. By study analysis will be performed for information only.
- SDMT scores and change from baseline will be summarized by visit-window and treatment in the combined FAS from studies G2301 and G2302. For the change from baseline values, a repeated measures mixed effects analysis adjusted for study, treatment, region, and SDMT baseline scores will be performed.
- Time to 6-month confirmed worsening of at least 20% in the timed 25-foot walk test (T25FW) will be analyzed in the combined FAS from studies G2301 and G2302, in a Cox proportional hazards model with study as stratum, treatment, and region as factors and the baseline T25FW-result as a continuous covariate. By study analysis will be performed for information only.
- Time to 6-month confirmed worsening of at least 20% in the 9-hole peg test (9HPT) will be analyzed in the combined FAS from studies G2301 and G2302, in a Cox proportional hazards model with study as stratum, treatment, and region as factors and baseline 9HPT-result as a continuous covariate. By study analysis will be performed for information only.
- The 6mCDI sustained until EOS will be analyzed in the same way as for the 6mCDI (as described in [Section 2.6.2.2](#))
- The disability status during the study will be summarized descriptively by treatment group (i.e., number and percent of patients improved, stable or worsened will be provided) and compared between treatment groups via a Chi-square test.
- For MS relapse characteristics, summary statistics will be presented. The proportion of patients hospitalized for relapse and the proportion of patients with severe relapses will be compared between treatment groups using a Chi-square test.
- For the presentation of descriptive statistics, ARR time based and ARR patient based will be reported by treatment group.

- Change in T2 lesion volume on MRI will be summarized by visit-window. Cross-sectional analyzes will be done by using a rank ANCOVA with treatment and region (factors), and baseline T2 volume as a continuous covariate.
- Number of new or enlarging T2 lesions on MRI between EOS and Month 12 will be analyzed in a negative binomial regression model, and presented similarly to that used for the annualized rate of new or enlarging T2 lesions. The number of new T2 lesions on the EOS scan relative to the Month 12 scan will be used as the response variable. The natural log of the time (in years) from the Month 12 scan to the EOS MRI scan will serve as the offset variable.
- Number of new or enlarging T2 lesions on MRI at yearly visits relative to baseline will be analyzed in a negative binomial regression model and presented similarly to that used for the annualized rate of new or enlarging T2 lesions. The number of new T2 lesions on the yearly MRI scan relative to the screening scan will be used as the response variable. The natural log of the time (in years) from the screening scan to the yearly MRI scan will serve as the offset variable. Due to the variable length of patient study participation, this analysis will only be performed for visits where there are at least a total of 100 patients with non-missing data on this endpoint. In case of non-convergence, region will be removed from the regression model.
- The analysis of ARBA is described in ([Section 2.6.2.6](#)) as supportive analysis to the key secondary endpoint of brain volume change.
- Proportion of patients free of clinical and MRI disease activity (No evidence of disease activity; NEDA-4) will be analyzed cross-sectionally at year 1 and year 2 in a logistic regression model with treatment and region as factor, and age, baseline EDSS, and number of Gd-lesions at baseline as covariates. A sensitivity analysis will be conducted considering all patients who discontinued from the study prior to the assessment timepoint, or have missing MRI assessments prior to the assessment timepoint, as not free of disease activity.
- EDSS, T25FW, 9HPT: The scores and their change from baseline values will be summarized by visit-window and treatment in the combined FAS from studies G2301 and G2302. For the change from baseline values, a repeated measures mixed effects analysis adjusted for study, treatment, region, and corresponding baseline values will be performed.
- NfL related secondary hypotheses are specified in [Section 2.6.2.5](#) as ‘supportive analysis’ for the key-secondary endpoint NfL.

